9.2 SAMPLE SIZE DETERMINATION

Sample size estimates were computed by hand and verified with PASS (Machin, Campbell, Fayers, & and Pinol, 1997) (Zar, 1984). Assuming a standard deviation of 1, we determined that an effective total of at least 117 medicated participants (Cohort 1) would be needed to demonstrate an effect size of 0.30 with 90% power at the 95% level of confidence using a within-group *t*-test. Similarly, at least 66 non-medicated participants (Cohort 2) would be needed to demonstrate an effect size of 0.40 with 90% power and 95% confidence. Incorporating a 10% dropout requires that at least $130 + 73 = 203$ patients are enrolled in the study. See Table 1 below for more details.

Table 1. Sample size estimates for various combinations of differences and standard deviations. In all cases, we assume 90% power and 95% confidence. The rows used to inform enrollment size for this trial have been highlighted in gray.

Absolute difference between follow-up and baseline	SD	Effect Size	Effective n
0.30	1.00	0.30	117
0.30	1.50	0.20	263
0.30	2.00	0.15	467
0.35	1.00	0.35	86
0.35	1.50	0.23	193
0.35	2.00	0.18	343
0.40	1.00	0.40	66
0.40	1.50	0.27	148
0.40	2.00	0.20	263
0.45	1.00	0.45	52
0.45	1.50	0.30	117
0.45	2.00	0.23	208
0.50	1.00	0.50	42
0.50	1.50	0.33	95
0.50	2.00	0.25	168

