9.1 STATISTICAL HYPOTHESES

The aim of the primary objective is to demonstrate a statistically significant difference on mean change in IRS “Overall severity of child’s problem in functioning and overall need for treatment” score, defined for each participant as the score measured on Day 28 minus the score measured at the baseline visit. In both the medicated and non-medicated cohorts, the statistical significance of the primary efficacy analysis will be assessed using a 2-sided paired *t*-test evaluated at the 95% level of confidence. The formulation of the null (H_0) and alternative (H_a) hypotheses are stated below, where μ_d refers to the true mean difference:

- $H_0: \mu_d = 0$
- $H_a: \mu_d \neq 0$.

If, within a particular cohort, the upper bound of the 95% confidence interval around the sample difference is smaller than 0, we will have sufficient evidence to reject H_0 and conclude that AKL-T01 plus Fengo improves ADHD symptoms in that cohort.

If the set of sample differences is non-normal, defined here as skewness larger than 1.5 in magnitude, the efficacy analysis will proceed as a non-parametric Wilcoxon signed rank test. Significance will be determined by evaluating the *W*-statistic at the 95% level of confidence.

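### Section 9.2 slightly misstates its sample-size figures: the completer numbers come from a normal approximation rather than the named t-test, and Cohort 2 enrolment was rounded down, leaving its power at about 89%

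*Combined protocol and SAP*

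**What the plan says.** Section 9.1 fixes the test. In each cohort, "the statistical significance of the primary efficacy analysis will be assessed using a 2-sided paired" t-test at the 95% confidence level.

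Section 9.2 gives the inputs and results:

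- Standard deviation: "Assuming a standard deviation of 1".
- Cohort 1: "an effective total of at least 117 medicated participants" for an effect size of 0.30, "with 90% power at the 95% level of confidence using a within-group *t*-test".
- Cohort 2: "at least 66 non-medicated participants (Cohort 2) would be needed to demonstrate an effect size of 0.40 with 90% power and 95% confidence".
- Enrolment: "Incorporating a 10% dropout requires that at least" 130 + 73 = 203 be enrolled.
- Table 1, 15 rows: "In all cases, we assume 90% power and 95% confidence".

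The section also says that the figures were worked out by hand and checked in PASS.

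Two other sections determine how dropout acts on the analysed number. Section 9.4.2 leaves out anyone without a baseline or Day 28 IRS score and allows no imputation. Section 7.2 says that withdrawn participants are not replaced.

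**The concern.** The numbers are presented as minima that secure 90% power for a named test. A reader who repeats the calculation for a two-sided paired t-test will not get 117 and 66. A reader who applies 10% dropout to 73 will not get back to 66.

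Both discrepancies fall on Cohort 2. That cohort is tested on its own under Sections 9.1 and 9.4.2, so Cohort 1 cannot make up for it. Because the primary analysis uses complete cases and nobody is replaced, enrolment is the only allowance for dropout. What is at stake is the accuracy of a stated power and a stated minimum, not the validity of any test.

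**Working it through.** **Inputs.** Two-sided alpha 0.05 (Section 9.1); power 90%, SD 1, effect sizes 0.30 and 0.40, dropout 10% (Section 9.2). The SD is read as that of the change score, as the layout of Table 1 implies.

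**Step 1: reproduce the plan's figures.** The one-sample normal formula is n = (z₀.₉₇₅ + z₀.₉₀)² / d², with (1.95996 + 1.28155)² = 10.507.

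- Cohort 1: 10.507 / 0.30² = 10.507 / 0.09 = 116.75, giving 117.
- Cohort 2: 10.507 / 0.40² = 10.507 / 0.16 = 65.67, giving 66.

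All 15 rows of Table 1 match this formula rounded to the nearest integer. Three of them were rounded down (343.10 to 343, 42.03 to 42, 168.12 to 168). A one-sided alpha does not fit: it gives 96 and 54.

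**Step 2: power under the named test.** Two-sided paired t-test, noncentral t with n − 1 degrees of freedom and noncentrality d√n:

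| Cohort | d | Completers | Power |
|---|---|---|---|
| 1 | 0.30 | 117 | 89.58% |
| 1 | 0.30 | 119 | 90.08% |
| 2 | 0.40 | 65 | 88.80% |
| 2 | 0.40 | 66 | 89.27% |
| 2 | 0.40 | 68 | 90.16% |

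The smallest numbers that reach 90% are 119 and 68, two more per cohort than stated. Across Table 1 the t-test number is 2 or 3 higher in every row.

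**Step 3: dropout.** Enrolment = completers / (1 − 0.10).

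- Cohort 1: 117 / 0.9 = 130 exactly.
- Cohort 2: 66 / 0.9 = 73.33, entered as 73. In reverse, 73 × 0.9 = 65.7, below 66.

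Rounding up gives 74, and 130 + 74 = 204 in total. If each participant drops out independently with probability 10%, 73 enrolled gives 66 or more completers with probability 0.55.

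**Step 4: power after dropout.** Cohort 1 has 89.6% at 117 completers. Cohort 2 has 89.1% at 65.7 completers. Averaging over binomial dropout gives 89.5% and 89.1%.

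**Step 5: share of each cause in Cohort 2.** The normal approximation accounts for 90 − 89.3 = 0.7 point. Rounding 73.33 down adds 89.27 − 88.80 = 0.47 point at most (66 against 65 completers), and about 0.1 point at the expected 65.7.

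**For reference.** Exact 90% t-test power with 10% dropout would correspond to 119 / 0.9 = 132.2, so 133, and 68 / 0.9 = 75.6, so 76: 209 in total against 203, a difference of 6 / 203 = 3.0%.

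**The case against.** The strongest reply is that the gap is too small to matter. Cohort 1's 89.6% is 90% at the whole-percent precision the protocol uses. Cohort 2 is short by about one point, and the completer numbers differ by two per cohort. That stands.

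The gap is also smaller than the uncertainty in the inputs. With 66 completers, t-test power is 90.4% if the SD is 0.98 and 88.1% if it is 1.02. With 8% dropout instead of 10%, 73 enrolled gives 89.8% and 130 enrolled gives 90.2%. Table 1 itself shows the required number for a 0.40 difference rising from 66 to 148 when the SD goes from 1 to 1.5. That stands too, and it limits the weight of the point.

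A further reply is that the section calls its figures estimates made by hand, and hand calculations often use normal quantiles. This explains the numbers but does not make them agree with the test named beside them. The PASS settings are not shown, so the documents do not reveal how that check came to agree.

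The rounding does not depend on the formula. Treating 65.7 as 66 to the nearest person is a fair reading of an estimate, but not of a number given as a minimum.

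A reader might infer from all this that the enrolment fails to deliver the planned power, or that Cohort 2 is underpowered. The documents do not support that: on the plan's own assumptions, power is between 88.8% and 89.6% at the completer numbers it implies.

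**Conclusion.** Section 9.2 is slightly wrong as written. The 117 and 66 are normal-approximation results given as t-test results, and 73 does not meet the section's own minimum of 66 completers after 10% dropout. The effect is about 0.4 point of power in Cohort 1, which is negligible, and about 1 point in Cohort 2.

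This rests on the plan's SD of 1, its effect sizes, its 10% dropout and the two-sided paired t-test, all taken as given. It says nothing about whether those assumptions are realistic.

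The point is one of precision and wording. No analysis, population, decision rule or conclusion depends on it, and it is not a reason to enrol more participants.

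**What to change.** Amend Section 9.2 in one or two sentences, without changing enrolment:

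- State that the completer numbers were obtained by the normal approximation.
- Restate the power of the two-sided paired t-test after 10% dropout as about 89.6% in Cohort 1 (effect size 0.30) and about 89% in Cohort 2 (effect size 0.40).
- Remove the words *at least* from the statement of 73 and 203 enrolled.

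The cost is a slightly less favourable stated power. If the sponsor prefers to keep the minimum wording for the completer target, rounding up alone gives 74 in Cohort 2 (204 in total). If it prefers to keep exact 90% power for the t-test, the corresponding completers are 119 and 68. Neither is needed to correct the text.

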9.3 POPULATIONS FOR ANALYSES

There are 3 populations defined for this study: intention-to-treat (ITT); per-protocol (PP); and, safety. The ITT and PP populations will be used for efficacy analyses, and the safety population will be used for the safety analysis. The success of the primary and secondary efficacy analyses will be determined within the ITT population.

9.3.1 INTENTION-TO-TREAT (ITT)

This population is defined as any participant enrolled in the study who receives a device. In the event that a medicated participant's clinician deems it necessary to end medication treatment (or vice versa), no correction will be made to that participant's cohort. Unless otherwise indicated, the ITT population will be used for all statistical analyses, tabular summaries, and data listings.

9.3.2 PER-PROTOCOL

This population is defined as any participant enrolled in the study who began AKL-T01 treatment, completed both the baseline and follow-up IRS assessments, and met a minimum level of compliance. Within both cohorts, an episode of play is approximately 25 minutes once per day, prescribed 5 days per week through the duration of the first treatment phase until Day 28. Compliance is defined as playing at least 50% of all possible episodes in the first treatment phase and is automatically monitored and transmitted back to sites by the device (see Section 6.3 of this document for additional details).

Additionally, the following participants will be excluded from the PP population:

- Participants in Cohort 1 who discontinue medication (or changed medication dosing/type) and participants in Cohort 2 who begin medication after the baseline visit but before Day 28 (i.e., crossovers)
- Participants who used prohibited/exclusionary medication or other treatments for ADHD during the course of the trial.

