During the 1-Month Break (Days 29 through 56) between AKL-T01 treatment phases, participants in Cohort 1 (stimulant) will continue to receive their current stimulant. In both cohorts, AKL-T01 will be suspended during this time. For both cohorts, during this time caretakers will continue to monitor their child's symptoms daily with AKL-X01.

During Treatment Phase 2 (Days 57 through 84), participants in Cohort 1 (stimulant) will continue to receive their current stimulant plus the addition of AKL-T01. Participants in Cohort 2 (no stimulant) will just receive AKL-T01. For both cohorts, during this time the caretakers will monitor their child's symptoms daily with AKL-X01

Objectives:

Primary: To understand the synergistic effects of combining AKL-T01 (with AKL-X01 symptom tracking) as adjunctive treatment to stimulant medication on impairment.

To understand the effects of AKL-T01 (with AKL-X01 symptom tracking) treatment in participants not recently on stimulant medication on impairment.

Secondary: To understand symptom and attentional effects of AKL-T01 (with AKL-X01 symptom tracking) in all participants (both Cohort 1 and Cohort 2).

Exploratory: To understand sustained benefits, through reduction of ADHD impairment and symptoms, following one month of AKL-T01 treatment (with AKL-X01 symptom tracking).

Endpoints:

Primary (Cohort 1, Cohort 2):

- 1) Overall change in clinician-reported Impairment Rating Scale (IRS) "Overall severity of child's problem in functioning and overall need for treatment" score from baseline to Day 28.

Secondary (Cohort 1, Cohort 2):

- 1) Overall change in ADHD-Rating Scale (ADHD-RS) total component score from baseline to Day 28.
- 2) Clinical Global Impression-Improvement (CGI-I) score at Day 28.
- 3) Overall change in Test of Variable Attention-Version 9 (TOVA) attention composite score (ACS) and certain constituent scores, from baseline to Day 28 (the specific constituent scores will be described in the SAP).

Exploratory (Cohort 1, Cohort 2):

- 1) Overall change in clinician-reported IRS "Overall severity of child's problem in functioning and overall need for treatment" score from baseline to Day 56 and from baseline to Day 84.
- 2) Overall change in ADHD-RS total component score from baseline to Day 56 and from baseline to Day 84.
- 3) CGI-I score at Day 56 and at Day 84.
- 4) Overall improvement in TOVA ACS and certain constituent scores, from baseline to Day 56 and from baseline to Day 84.

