- 6) Melatonin, provided that use is intermittent and not every day and is only taken at night

Prohibited Medications, taken 30 days prior to Baseline visit and throughout the duration of the trial include:

- 1) Amphetamines (**if participant is enrolled into Cohort 2**)
- 2) Methylphenidates (**if participant is enrolled into Cohort 2**)
- 3) SSRIs (e.g., fluoxetine, paroxetine)
- 4) MAOIs (monoamine oxidase inhibitors)
- 5) Mood stabilizers (e.g., lithium, valproate, quetiapine)
- 6) Antipsychotics (e.g., risperidone, olanzapine)
- 7) Anticonvulsants (e.g., phenobarbital, phenytoin, primidone)
- 8) Anticoagulants
- 9) Dextromethorphan
- 10) Halogenated anesthetics

- 11) Tricyclic antidepressants
- 12) Atomoxetine
- 13) Guanfacine
- 14) Clonidine
- 15) Phenylbutazone
- 16) Sedating antihistamines
- 17) Decongestants with stimulant properties

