9.4.2 ANALYSIS OF THE PRIMARY EFFICACY ENDPOINT(S)

The primary efficacy endpoint for each participant is the change in IRS score from baseline to Day 28, defined as the score on Day 28 minus the score at baseline. Missing data will not be imputed. If a participant is missing either the baseline or Day 28 IRS assessment, that participant will be excluded from the analysis. Within each cohort, the ITT population is the primary efficacy analysis population. Additional per-protocol analyses will be performed on the per-protocol population.

Statistical significance of the change in IRS will be determined using a paired *t*-test. No adjustment for covariates will take place for the primary efficacy analysis, although additional analyses may be requested at the discretion of the investigators. Details will be provided in the SAP.

The results of the primary efficacy analysis will be summarized by cohort as mean change (95% confidence interval) and p-value. If the upper bound of the 95% confidence interval is smaller than 0 in a particular cohort, we will conclude that significance is achieved within that cohort.

Outliers will be determined clinically and identified by an independent third party, with confirmation coming from the PI. If outliers are identified for a given endpoint, a sensitivity analysis will be performed without the outlier.

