9.4.3 ANALYSIS OF THE SECONDARY ENDPOINT(S)

The following secondary efficacy endpoints will be tested using the same technique outlined for the primary efficacy analysis: (1) change in sum of ADHD-RS component scores from baseline to Day 28; (2) CGI-I score at Day 28; and, (3) change in TOVA ACS and certain constituents, from baseline to Day 28. The ITT population will be used for all secondary efficacy endpoints with the same analyses being repeated on the per-protocol population.

Family-wise error rate will be controlled using a hierarchical testing strategy. Within each cohort, the maximum allowable Type I error rate will be set to 0.05.

If the primary efficacy endpoint is significant at the 0.05 confidence level, the secondary efficacy endpoints will be tested sequentially in the order in which they appear above, starting with (1) change in autocalculated sum of ADHD-RS Total. If the test for (1) is significant at the 0.05 confidence level, the test for (2) CGI-I score at Day 28 will proceed. If the test for (2) is significant at the 0.05 confidence level, the test for (3) change in TOVA constituents from baseline to Day 28 will proceed, starting with Ex-Gaussian Tau Total, and then to API/ACS, Commission Errors Standard Score H2, RT Variability Standard Score Total, RT Mean Standard Score H1, D-Prime Standard Score H2, and Omission Errors Standard Score H2, in this order. At any point, if the test of a secondary efficacy endpoint fails to achieve significance at the 0.05 confidence level, only nominal p-values will be reported for that endpoint and for all subsequent secondary efficacy endpoints.

If the primary efficacy endpoint is not significant at the 0.05 confidence level, only nominal p-values will be reported for all secondary efficacy endpoints.

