9.4.9 EXPLORATORY ANALYSES

The following exploratory analysis endpoints will be investigated and descriptive statistics will be summarized in the medicated and non-medicated cohorts using the ITT population:

- 1) Overall change in clinician-reported IRS “Overall severity of child’s problem in functioning and overall need for treatment” score from baseline to Day 56 and from baseline to Day 84.
- 2) Overall change in ADHD-RS total component score from baseline to Day 56 and from baseline to Day 84.
- 3) CGI-I score at Day 56 and at Day 84.
- 4) Overall improvement in TOVA ACS and certain constituent scores, from baseline to Day 56 and from baseline to Day 84.
- 5) Overall change in Test of Silent Reading Efficiency and Comprehension (ToSREC) from baseline to Day 28 and from baseline to Day 84, using the appropriate ToSREC form.
- 6) Overall change in Mathematics Fluency and Calculation Tests (MFaCTs) from baseline to Day 28 and from baseline to Day 84, using the appropriate MFaCTs form.

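### The second per-protocol exclusion has no Day 28 limit, so treatment started after the outcome was measured removes a child from the Day 28 per-protocol analysis

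*Combined protocol and SAP*

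**What the plan says.** Section 9.3.2 defines the PP population by three requirements: treatment begun, baseline and follow-up IRS completed, and a play threshold ("Compliance is defined as playing at least 50% of all possible episodes in the first treatment phase"). Two medication exclusions follow.

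- The first removes Cohort 1 children who stop or change their stimulant and "participants in Cohort 2 who begin medication after the baseline visit but before Day 28 (i.e., crossovers".
- The second removes "Participants who used prohibited/exclusionary medication or other treatments for ADHD during the course of the trial". It carries no date limit.

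Section 6.4 lists "Prohibited Medications, taken 30 days prior to Baseline visit and throughout the duration of the trial include" amphetamines and methylphenidates for Cohort 2, and atomoxetine, guanfacine and clonidine for everyone. Section 4.4 ends participation at Day 84.

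PP has two uses. For the primary endpoint, section 9.4.2 says "Additional per-protocol analyses will be performed on the per-protocol population". For the secondary endpoints, section 9.4.3 has ITT as the main analysis "with the same analyses being repeated on the per-protocol population". All of these endpoints are at Day 28. For the exploratory endpoints, which include every Day 56 and Day 84 efficacy measure, section 9.4.9 says "descriptive statistics will be summarized in the medicated and non-medicated cohorts using the ITT population". Section 9.3 has success judged in ITT.

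**The concern.** A child's Day 28 change is fixed once the Day 28 IRS has been scored. Nothing that happens afterwards can contaminate it, so a later treatment start is no reason to remove it. It can, however, be a consequence of it. The synopsis says of Days 29 to 56: "In both cohorts, AKL-T01 will be suspended during this time". A family whose child has not improved may look for another treatment in that month. If so, the exclusion preferentially removes poor Day 28 results, and the PP mean looks better than it should.

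What is at stake is the supporting analysis. The trial has no control arm, and a PP result that agrees with ITT will tend to be read as reassurance. That reassurance is weaker if membership of the PP population depends partly on the outcome.

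**Working it through.** **1. The two windows applied to the same child.** Each row is a literal reading of sections 9.3.2 and 6.4.

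| Event | First exclusion | Second exclusion | In the Day 28 PP analysis? |
|---|---|---|---|
| Cohort 2, stimulant started Day 15 | removes | removes | no |
| Cohort 2, stimulant started Day 40 | does not apply (after Day 28) | removes (prohibited all trial) | no |
| Either cohort, atomoxetine, guanfacine, clonidine or another ADHD treatment added Day 40 | does not apply, or not clearly | removes | no |
| Cohort 1, stimulant dose changed Day 40 | appears not to apply | does not clearly apply (stimulants are allowed) | apparently yes |

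Row 2 shows that the first exclusion's Day 28 limit has no effect for that child. No analysis listed in sections 9.4.2, 9.4.3 or 9.4.9 needs a PP population defined beyond Day 28.

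**2. The plan's own figure.** Section 9.2 assumes SD 1, two-sided 5% and 90% power. For Cohort 2, n = ((1.960 + 1.282)/0.40)² = 65.7, rounded up to the stated 66. The planned effect of 0.40 with SD 1 is therefore a fair base for the illustration.

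**3. Size of the shift.** Model the change X (Day 28 minus baseline, negative is better) as normal with mean −0.40 and SD 1, and call a child with X ≥ 0 a non-improver. This is an approximation for a single rating item. A fraction p of non-improvers and a fraction q of improvers start treatment after Day 28 and are dropped. The documents give neither, so both are assumptions.

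- P(X ≥ 0) = Φ(−0.40) = 0.3446
- A = E[X; X ≥ 0] = φ(0.40) − 0.40 × 0.3446 = 0.3683 − 0.1378 = 0.2304
- B = E[X; X < 0] = −0.40 − 0.2304 = −0.6304
- PP mean = (−0.40 − pA − qB) / (1 − 0.3446p − 0.6554q)

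Results:

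- p = 2%, q = 0: −0.4046/0.9931 = −0.407
- p = 10%, q = 0: −0.4230/0.9655 = −0.438
- p = 20%, q = 0: −0.4461/0.9311 = −0.479
- p = 10%, q = 5%: −0.3915/0.9328 = −0.420
- p = q, any value: −0.40, no bias
- p = 0, q = 10%: −0.3370/0.9345 = −0.361, bias reversed

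Few children are involved. With q = 0, 66 × 0.0345 = 2.3 children are dropped at p = 10%, and 66 × 0.0689 = 4.5 at p = 20%.

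**The case against.** **Late starts may be rare.** The synopsis requires the investigator to judge it acceptable for the child to stay on the same dose, or off stimulants, throughout. Section 5.3 asks Cohort 2 not to begin medication. Section 6.4 does not permit new non-drug ADHD treatment, and section 5.2 excludes children who plan to change behavioural therapy. This stands. At 2% of non-improvers the shift is under 0.01.

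**The drafters may have meant a Day 28 cut-off all along.** Possibly, but the text does not say so, and the different wording of the two adjacent exclusions invites the literal reading.

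**PP does not decide success.** This also stands, and it limits a stronger inference. A reader might work out that, with no true effect and 20% of non-improvers dropped, PP would show a false improvement about 10% of the time at n = 66 instead of 2.5%, and conclude that the trial could falsely confirm its result that often. The documents do not support that. ITT must succeed first, and with no true effect it does so in the favourable direction only about 2.5% of the time, so false agreement between the two cannot exceed about 2.5% per cohort.

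**Cohort 1.** A reader might apply the same rates there. But late stimulant changes in Cohort 1 appear to stay in, so only an added non-stimulant or other ADHD treatment would trigger removal. The first exclusion can be parsed so that its date limit covers only Cohort 2, which leaves the Cohort 1 reading open.

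**The play threshold.** A reader might also fault PP for mixing low play with medication change. A compliance threshold is ordinary in a PP population, and the protocol nowhere presents PP as a test that isolates medication change.

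**Conclusion.** The point holds as a drafting flaw in a supporting analysis: the second PP exclusion reaches to Day 84 while every PP endpoint is at Day 28, so children can be removed because of events after their outcome was measured. Severity is minor.

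The direction and size in this trial are unknown. The shift from 0.40 to about 0.44 or 0.48 in Cohort 2 rests on assumed start rates of 10% or 20% among non-improvers and none among improvers. Smaller or more even rates shrink it to nothing, and starts confined to improvers would make PP conservative. The ITT primary test, its success rule and the hierarchical testing of the secondary endpoints are not affected. Section 9 also refers to a separate SAP, which may clarify the window; the supplied text does not.

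**What to change.** In section 9.3.2, limit the second exclusion to prohibited medication or other ADHD treatment used after baseline and before the child's Day 28 IRS. Tying it to the assessment date rather than to nominal Day 28 allows for the ±3-day visit window in section 1.3. The cost is one phrase. Concomitant medication is already reviewed at each visit, and the first exclusion already needs medication changes placed before or after Day 28. Sample size, alpha and visits do not change.

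Optionally, as non-gating support, report the children who changed ADHD treatment before the Day 28 IRS by cohort and direction (start, increase, switch, decrease, stop), and rerun the ITT complete-case analysis without them. This costs one extra run per cohort and has two limits. If an assumed 10% are removed, power at the planned effects falls from 89.6% to 86.1% in Cohort 1 (n = 117 to 105) and from 89.3% to 85.6% in Cohort 2 (n = 66 to 59). It also still removes children for a post-baseline event that may follow non-improvement, so it should be read beside ITT and not in place of it.
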